2 PROTOCOL SUMMARY

Title:	Early Feasibility Study for Evaluation of the TraceIT Tissue Spacer for Creating Space Between the Duodenum and Pancreas in Patients with Localized Pancreatic Cancer Undergoing a Course of Radiation Therapy: The TIPS Pilot Study
Device:	TraceIT Tissue Spacer consists of a pre-filled glass syringe containing the absorbable radiopaque cross-linked polyethylene glycol (PEG) hydrogel spacer and a delivery mechanism (syringe and needle) packaged in a single use kit.
Indication:	TraceIT Tissue Spacer is a radiopaque hydrogel material intended to temporarily position the duodenum away from the pancreas in subjects undergoing RT for treatment of pancreatic cancer and in creating this space it is the intent of TraceIT Tissue Spacer to reduce the radiation dose delivered to the duodenum during radiotherapy. When used as a spacer, the TraceIT hydrogel radiographically marks the area for radiotherapy planning and localization.
Study Objective:	To evaluate the feasibility, radiotherapy benefits, and safety when using TraceIT Tissue Spacer to create space between the pancreas and duodenum.
Study Design:	Multicenter prospective, single-arm early feasibility study. Six (6) subjects with localized (resectable, borderline resectable or locally advanced) pancreatic cancer (defined per NCCN guidelines) having completed induction chemotherapy if required and for whom a course of radiotherapy (RT) is indicated will be enrolled. Enrolled subjects will undergo placement of intrapancreatic fiducial markers and peri-duodenal administration of TraceIT hydrogel within the same endoscopic ultrasound transduodenal procedure. The hydrogel will be distributed in small volumes (generally ~1 to 2 mL and up to a total of 20 mL) at several areas along the proximal portion of the duodenum in the areas closest to the head of the pancreas (HOP). RT simulation planning will be performed prior to and following TraceIT placement for evaluation and comparison of duodenal dose / dose distribution and to assess differences in RT dosing parameters. The pre- and post-TraceIT injection simulation planning will be performed using the identical technique and similar set-up, and with appropriate respiratory motion control (e.g., feedback-guided inspiratory breath-hold gating, end expiratory gating during free breathing or abdominal compression as appropriate).

	
In accordance with standard medical practice, within 2-6 weeks after completion of therapy, subjects will be restaged to determine whether they may progress to surgery. If surgical resection is attempted and successful, pathological data will be recorded within the study eCRF.
 
All subjects will be evaluated at minimum 3 and 6 months post-TraceIT administration. An MR will be performed at the 6 month visit to evaluate for TraceIT presence. Throughout the duration of the study, subjects will be clinically evaluated and assessed for duodenal adverse events using the grading of the NCI Common Terminology Criteria for Adverse Events (CTCAE v4). Quality of life data will be collected using the EORTC QLQ-PAN26 and QLQ-C30 questionnaires.
 
Additional longer-term follow-up clinic visits will be performed in accordance with standard of care, at minimum, 12 and 18 months.

Safety Endpoints:	
Subjects will be monitored for adverse events and radiotherapy (RT) toxicity (using CTCAE v4) and in particular for the safety endpoint defined as “TraceIT administration procedure-related events which result in a delay in initiation of RT” as reviewed and adjudicated by a Clinical Events Committee.

Effectiveness Endpoints:	
Effectiveness endpoints of interest for this study are as follows:
 
 • Feasibility: Feasibility will be defined to be Technical Success; i.e., the ability to place TraceIT and create space between the duodenum and HOP. • Radiotherapy Benefits: Will be assessed via comparison of pre- and post-TraceIT administration RT plans with consideration of the following: ability to maintain safe duodenal dose constraints, percent/volume of GTV/PTV receiving prescription dose and overall duodenal dose/ dose distribution. 
Additional data collection will include:
 
 • Incidence of resection • Histology of duodenal tissues when resection is performed • Incidence of acute (within 3 months) and late (>3 months) duodenal toxicity (for unresected subjects) • Theoretical dose escalation from post-TraceIT treatment plan • TraceIT persistence (at 6-months post-treatment in nonresected subjects) • Change from baseline in EORTC QoL (QLQ-C30) and QLQ-PAN26 • Comparability of visualization of the fiducial marker and TraceIT hydrogel using a standardized visualization score • Progression free and overall survival through follow-up

Inclusion Criteria:	
Subjects must meet all of the following criteria to be eligible for participation in the study:
 
 1. Age ≥ 18 years old 2. Biopsy-confirmed localized pancreatic cancer in the head or neck of the pancreas that is able to be visualized via CT or other imaging modality (e.g., PET) with no evidence of distant metastasis (AJCC clinical stage IA-III) as defined by the NCCN guidelines: 
Printed by [name] on 7/20/2017 7:33:47 AM. For personal use only. Not approved for distribution. Copyright © 2017 National Comprehensive Cancer Network, Inc. All Rights Reserved.
 
NCCN Guidelines Version 2.2017 Pancreatic Adenocarcinoma
 
CRITERIA DEFINING RESECTABILITY STATUS¹
 
  
 Resectability Status	Arterial	Venous	
   
 Resectable	No arterial tumor contact (celiac axis [CA], superior mesenteric artery [SMA], or common hepatic artery [CHA]).	No tumor contact with the superior mesenteric vein (SMV) or portal vein (PV) or $\leq 180^\circ$ contact without vein contour irregularity.	
 
 Borderline Resectable²	 
 Pancreatic head/uncinate process: 
 Solid tumor contact with CHA without extension to celiac axis or hepatic artery bifurcation allowing for safe and complete resection and reconstruction. Solid tumor contact with the SMA of $\leq 180^\circ$. Solid tumor contact with varied arterial anatomy (ex: accessory right hepatic artery, replaced CHA, and the origin of replaced or accessory artery) and the presence and degree of tumor contact should be noted if present as it may affect surgical planning. Pancreatic body/tail: 
 Solid tumor contact with the CA of $\leq 180^\circ$. Solid tumor contact with the CA of $\leq 180^\circ$ without involvement of the aorta and with intact and uninolved gastroduodenal artery thereby permitting a modified Appleby procedure (some members prefer this category to be in the unresectable category). 	 
 Solid tumor contact with the SMV or PV of $>180^\circ$, contact of $\geq 180^\circ$ with contour irregularity of the vein or thrombosis of the vein but with suitable vessel proximal and distal to the site of thrombosis allowing for safe and complete resection and vein reconstruction. Solid tumor contact with the inferior vena cava (IVC). 	
 
 Unresectable²	 
 Distal metastasis (including non-regional lymph node metastasis) Head/uncinate process: 
 Solid tumor contact with SMA $>180^\circ$ Solid tumor contact with CA $>180^\circ$ Solid tumor contact with the first jejunal SMA branch Body and tail: 
 Solid tumor contact of $>180^\circ$ with the SMA or CA Solid tumor contact with the CA and aortic involvement 	 
 Head/uncinate process: 
 Unreconstructable SMV/PV due to tumor involvement or occlusion (can be due to tumor or bland thrombus) Common hepatic artery (CHA) and most proximal draining jejunal branch into SMV Body and tail: 
 Unreconstructable SMV/PV due to tumor involvement or occlusion (can be due to tumor or bland thrombus) 	
  
 
¹AI-Hawary MM, Francis IR, Chari ST, et al. Pancreatic ductal adenocarcinoma radiology reporting template: consensus statement of the Society of Abdominal Radiology and the American Pancreatic Association. Radiology 2014 Jan; 270(1):248-260.
 
²Some tumors may be resectable with extensive lymphadenectomy and/or resection of peripancreatic vessels (typically seen following neoadjuvant therapy); this finding should be reported on the staging and follow-up scans. Decision on resectability status should be made in these patients, in consensus at multidisciplinary meetings/discussions.
 
Note: All recommendations are category 2A unless otherwise indicated. Clinical Trials: NCCN believes that the best management of any patient with cancer is in a clinical trial. Participation in clinical trials is especially encouraged.
 
Version 2.2017, 04/27/17 © National Comprehensive Cancer Network, Inc. 2017. All rights reserved. The NCCN Guidelines® and this illustration may not be reproduced in any form without the express written permission of NCCN.
 
PANC-B
 
 3. Tumor is clearly delineable from duodenum and no clear evidence of invasion of the duodenum is seen at time of EUS performed for either diagnosis or fiducial placement. 4. Subject is able to comply with motion management guidelines 5. Radiotherapy or chemoradiotherapy for treatment of the disease is indicated 6. In Investigator's opinion, medically fit to undergo endoscopy for fiducial marker implantation and TraceIT administration 7. Subjects Screening/Baseline laboratory testing must meet the following laboratory value criteria: 
 a. White blood cell count: $\geq 3.0 \times 10^9/L$ b. Absolute neutrophil count (ANC): $\geq 1.5 \times 10^9/L$ c. Platelets: $\geq 100 \times 10^9/L$ d. Total bilirubin: ≤ 2.0 times upper limit of normal (ULN) e. AST and ALT: ≤ 3.0 times institutional upper normal limit f. Serum creatinine: < 1.5 times ULN g. INR: < 1.5 h. Serum pregnancy: Negative i. Hemoglobin: ≥ 8.0 g/dL 8. Zubrod Performance Status 0-2 9. Subject or authorized representative, has been informed of the nature of the study and has provided written informed consent, approved by the appropriate Institutional Review Board (IRB) of the respective clinical site 10. Life expectancy of at least 9 months 	Resectability Status	Arterial	Venous	Resectable	No arterial tumor contact (celiac axis [CA], superior mesenteric artery [SMA], or common hepatic artery [CHA]).	No tumor contact with the superior mesenteric vein (SMV) or portal vein (PV) or $\leq 180^\circ$ contact without vein contour irregularity.	Borderline Resectable²	
 Pancreatic head/uncinate process: 
 Solid tumor contact with CHA without extension to celiac axis or hepatic artery bifurcation allowing for safe and complete resection and reconstruction. Solid tumor contact with the SMA of $\leq 180^\circ$. Solid tumor contact with varied arterial anatomy (ex: accessory right hepatic artery, replaced CHA, and the origin of replaced or accessory artery) and the presence and degree of tumor contact should be noted if present as it may affect surgical planning. Pancreatic body/tail: 
 Solid tumor contact with the CA of $\leq 180^\circ$. Solid tumor contact with the CA of $\leq 180^\circ$ without involvement of the aorta and with intact and uninolved gastroduodenal artery thereby permitting a modified Appleby procedure (some members prefer this category to be in the unresectable category). 	
 Solid tumor contact with the SMV or PV of $>180^\circ$, contact of $\geq 180^\circ$ with contour irregularity of the vein or thrombosis of the vein but with suitable vessel proximal and distal to the site of thrombosis allowing for safe and complete resection and vein reconstruction. Solid tumor contact with the inferior vena cava (IVC). 	Unresectable²	
 Distal metastasis (including non-regional lymph node metastasis) Head/uncinate process: 
 Solid tumor contact with SMA $>180^\circ$ Solid tumor contact with CA $>180^\circ$ Solid tumor contact with the first jejunal SMA branch Body and tail: 
 Solid tumor contact of $>180^\circ$ with the SMA or CA Solid tumor contact with the CA and aortic involvement 	
 Head/uncinate process: 
 Unreconstructable SMV/PV due to tumor involvement or occlusion (can be due to tumor or bland thrombus) Common hepatic artery (CHA) and most proximal draining jejunal branch into SMV Body and tail: 
 Unreconstructable SMV/PV due to tumor involvement or occlusion (can be due to tumor or bland thrombus)
Resectability Status	Arterial	Venous											
Resectable	No arterial tumor contact (celiac axis [CA], superior mesenteric artery [SMA], or common hepatic artery [CHA]).	No tumor contact with the superior mesenteric vein (SMV) or portal vein (PV) or $\leq 180^\circ$ contact without vein contour irregularity.											
Borderline Resectable²	
 Pancreatic head/uncinate process: 
 Solid tumor contact with CHA without extension to celiac axis or hepatic artery bifurcation allowing for safe and complete resection and reconstruction. Solid tumor contact with the SMA of $\leq 180^\circ$. Solid tumor contact with varied arterial anatomy (ex: accessory right hepatic artery, replaced CHA, and the origin of replaced or accessory artery) and the presence and degree of tumor contact should be noted if present as it may affect surgical planning. Pancreatic body/tail: 
 Solid tumor contact with the CA of $\leq 180^\circ$. Solid tumor contact with the CA of $\leq 180^\circ$ without involvement of the aorta and with intact and uninolved gastroduodenal artery thereby permitting a modified Appleby procedure (some members prefer this category to be in the unresectable category). 	
 Solid tumor contact with the SMV or PV of $>180^\circ$, contact of $\geq 180^\circ$ with contour irregularity of the vein or thrombosis of the vein but with suitable vessel proximal and distal to the site of thrombosis allowing for safe and complete resection and vein reconstruction. Solid tumor contact with the inferior vena cava (IVC). 											
Unresectable²	
 Distal metastasis (including non-regional lymph node metastasis) Head/uncinate process: 
 Solid tumor contact with SMA $>180^\circ$ Solid tumor contact with CA $>180^\circ$ Solid tumor contact with the first jejunal SMA branch Body and tail: 
 Solid tumor contact of $>180^\circ$ with the SMA or CA Solid tumor contact with the CA and aortic involvement 	
 Head/uncinate process: 
 Unreconstructable SMV/PV due to tumor involvement or occlusion (can be due to tumor or bland thrombus) Common hepatic artery (CHA) and most proximal draining jejunal branch into SMV Body and tail: 
 Unreconstructable SMV/PV due to tumor involvement or occlusion (can be due to tumor or bland thrombus) 											

Exclusion Criteria	
Subjects who meet any of the following criteria are not eligible for participation in the study:
 
 1. Patients for whom radiotherapy is contraindicated 2. Previous thoracic or abdominal radiotherapy 3. Any GI abnormality that would interfere with the ability to access the injection site 4. Presence of tumor invasion of the duodenum detected on EUS at time of biopsy 5. Previous Whipple procedure or other resection of pancreatic tumor prior to screening 6. Active gastroduodenal ulcer or uncontrolled watery diarrhea 7. History of Chronic Renal Failure 8. Documented history of uncontrolled diabetes (i.e., symptomatic hyperglycemia that cannot be medically managed, fasting blood glucose level above 300 mg/dL, and/or frequent swings between hyperglycemia and hypoglycemia) 9. Currently enrolled in another investigational drug or device trial that clinically interferes with this study 10. Unable to comply with the study requirements or follow-up schedule 11. Any condition or comorbidity that the Investigator believes would interfere with the intent of the study or would make participation not in the best interest of the subject 12. Women who are pregnant or breast-feeding; women of child-bearing age must use contraceptives
Screening/Baseline: (within 45 days prior to planned TraceIT hydrogel injection)	
Subjects who appear to meet the eligibility criteria will be consented for the study and will undergo screening. Information to be collected at screening and baseline includes:
 
 • Demographic information: date of birth, weight and height, race • Disease documentation: tumor location, initial resectability status, tumor staging, largest pre-treatment dimension of tumor (cm) • Medical/Surgical History/Current status: concomitant medical conditions, prior medical conditions, prior surgeries, prior therapies (e.g., induction chemotherapy) • Physical Examination: including sitting blood pressure, pulse, temperature, weight, anticoagulation status, Zubrod Performance Score • Laboratory testing for hematology plus platelets, creatinine, AST/ALT and bilirubin and baseline serum carbohydrate antigen (CA) 19-9 • Pregnancy test for women of child-bearing potential. • EORTC-QLQ-C30 and QLQ-PAN26 • Assessment of baseline duodenal symptoms per NCI CTCAE • Baseline concomitant medications

Initial RT Planning & Documentation	
Subjects who appear to meet the inclusion criteria and do not present with any of the exclusion criteria will undergo a CT for baseline RT Planning.
 
The initial minimum target dose will be 33 Gy in 5 fractions (or an equivalent biologically effective dose if >5 fractions is being delivered). CT simulation will be performed with immobilization.
 
Target dose constraints for OAR include:
 
  
 Organs at Risk (OAR)	Dose Constraint*	
   
 Proximal duodenum, proximal stomach and small bowel	V15Gy<9cc, V20Gy<3 cc, and V35Gy<1cc A duodenal maximum dose of \leq32 Gy should initially be attempted	
 
 Stomach	V12Gy<50%, V35Gy<1cc	
 
 Liver	V12Gy<50%	
 
 Combined Kidneys	V12Gy<75%;	
 
 Spinal Cord	V8Gy<1 cc	
  
 
*or biologically equivalent dose constraints for >5 fractions
 
Radiographic tumor-vessel interface will be documented.
 
Other dosimetric data to be collected include: V5 (volume (cc) of the duodenum receiving 5 Gy or more), V10, V15, V20, V25, V30, V35, V40, duodenal mean/maximum doses, GTV/PTV minimum/mean/maximum doses as well as GTV/PTV volume, and total duodenal volume.
	Organs at Risk (OAR)	Dose Constraint*	Proximal duodenum, proximal stomach and small bowel	V15Gy<9cc, V20Gy<3 cc, and V35Gy<1cc A duodenal maximum dose of \leq 32 Gy should initially be attempted	Stomach	V12Gy<50%, V35Gy<1cc	Liver	V12Gy<50%	Combined Kidneys	V12Gy<75%;	Spinal Cord	V8Gy<1 cc
Organs at Risk (OAR)	Dose Constraint*												
Proximal duodenum, proximal stomach and small bowel	V15Gy<9cc, V20Gy<3 cc, and V35Gy<1cc A duodenal maximum dose of \leq 32 Gy should initially be attempted												
Stomach	V12Gy<50%, V35Gy<1cc												
Liver	V12Gy<50%												
Combined Kidneys	V12Gy<75%;												
Spinal Cord	V8Gy<1 cc												
Index Procedure: Fiducial Placement/ TraceIT Hydrogel Injection	
 Ability to access injection site and inject TraceIT material Average duodenal space measurements on CT measured at 3 points along the head of the pancreas TraceIT Injection Procedure Duration Ease of Device Use Device malfunctions Adverse Events per NCI CTCAE ver. 4.0 												
Follow-up for Non-Injection Subjects (30 days +7 days or until resolution/stabilization of an adverse event if applicable)	
A “Non-Injection” Subject is a subject who was intended to be treated with TraceIT, but in whom TraceIT was unable to be injected. No further image collection is required for these subjects.
 
 30 Day Visit to include: 
 Physical Assessment: including sitting blood pressure, pulse, temperature, and Zubrod Performance Score Assessment of Intestinal Adverse Events documented using CTCAE criteria Other Adverse Events per NCI CTCAE Changes in concomitant medications used to treat intestinal symptoms 												

Post-injection RT Planning (less than 28 days following Index Procedure)	
 Repeat CT Planning Imaging using the same number of beams and set-up as Pre-injection planning Dosimetric data to be collected include: V5 (volume (cc) of the duodenum receiving 5 Gy or more), V10, V15, V20, V25, V30, V35, V40, duodenal mean/maximum doses, GTV/PTV minimum/mean/maximum doses as well as GTV/PTV volume, and total duodenal volume Theoretical dose escalation (maximum dose to GTV while maintaining duodenal dose constraints)
RT Initiation	
 RT must be initiated no later than (NLT) 28 days following TraceIT administration RT should be initiated no sooner than (NST) 1 week from last chemotherapy dose
Final RT Fraction	
 Physical Assessment (including vital signs, weight and Zubrod Performance score) EORTC-QLQ-C30 and QLQ-PAN26 Assessment of duodenal focused Adverse Events documented using NCI CTCAE Other Adverse Events per NCI CTCAE Changes in concomitant medications used to treat intestinal symptoms
Week 2-6 Following Completion of RT (Restaging & Evaluation for Potential Resection at time of CT)	
 Physical Examination: including sitting blood pressure, pulse, temperature, weight, anticoagulation status, Zubrod Performance Score CT for restaging (also will evaluate TraceIT Persistence) Assessment of duodenal focused Adverse Events documented using NCI CTCAE Other Adverse Events per NCI CTCAE Changes in concomitant medications used to treat intestinal symptoms CA-19-9 level Pancreaticoduodenectomy should be targeted to be performed within 8 weeks after the completion of RT if applicable. 
Restaging and determination of resectability will be performed in accordance with the standard institutional practices.

Resected Subjects (At time of resection)	
 Physical Examination: including sitting blood pressure, pulse, temperature, weight, anticoagulation status, Zubrod Performance Score Assessment of duodenal focused Adverse Events documented using NCI CTCAE if available Other Adverse Events per NCI CTCAE if available Changes in concomitant medications used to treat intestinal symptoms

Resected Subjects (Histopathology record)	
 Incidence of complete or partial response (Path PR and Path CR) Pathologic duodenal damage score rated by a local board-certified gastrointestinal surgical pathologist using the methods outlined by Verma et al.,¹ where: 
 1=no/minimal signs of mucosal damage: villi remain long and slender, epithelial cells have abundant eosinophilic cytoplasm with few mitotic figures, and the lamina propria have normal amounts of inflammatory cells including few or no neutrophils. 2=moderate damage where villi are blunted or absent, epithelial cells have reactive/reparative changes with basophilic cytoplasm, increase mitotic figures, and/or small erosions or focal ulcerations; the lamina propria show increased inflammation including eosinophils and neutrophils. 3=severe damage with diffuse epithelial damage absent with or without extensive ulcerations and residual surviving epithelium displaying marked reactive/reparative changes; lamina propria replaced with granulation tissue and/or overlying fibrinoid inflammatory exudates with numerous neutrophils or marked damage.
Additional Follow-up at Month 3 (\pm 14 days) and Month 6 (\pm 14 days) Post-Index Procedure	
 Physical Examination: including sitting blood pressure, pulse, temperature, weight, anticoagulation status, Zubrod Performance Score Unresected subjects only: MRI at Month 6 post-index procedure Assessment of duodenal focused Adverse Events documented using NCI CTCAE Other Adverse Events per NCI CTCAE PAN26, EORTC-QLQ-C30 Changes in concomitant medications used to treat intestinal symptoms Post-surgical complications in resected subjects
Longer-Term Follow-up	Following the 6-month visit, subjects will be followed through to 18 months in accordance with standard of care with at minimum clinical visits performed at Month 12 and Month 18 (\pm 28 days for each visit).
Clinical Events Committee (CEC)	A CEC will be appointed by Augmenix. Members of the CEC will include physicians with a specialty in treating patients with pancreatic cancer including a radiation oncologist and a gastroenterologist. These physicians will be independent of the study Investigators and will be responsible for interim review and classification of adverse events observed and will review data related to the conduct and quality of the study. The CEC may make formal recommendations for protocol changes to mitigate risk of adverse events.

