9 ADVERSE EVENTS

9.1 Definitions

Adverse Event (AE): Any untoward medical occurrence in a subject that is of new onset or has become worse including consequences of medical therapy resulting from a potential study-related delay in radiation treatment

Adverse events are to be recorded from initiation of fiducial marker placement through the 18 month visit.

Adverse Device Effect (ADE): An adverse event that is believed to have been caused by or is associated with the device.

Serious Adverse Event (SAE): An adverse event that:

- a. Led to death
- b. Resulted in a life-threatening illness or injury
- c. Resulted in a permanent impairment of a body structure or a body function
- d. Resulted in in-patient hospitalization or prolongation of existing hospitalization
- e. Resulted in medical or surgical intervention to prevent permanent impairment to body structure or a body function

The investigator will report serious events to the Sponsor and to his/her IRB per the institution's requirements and as specified in section 8.1.1.

Serious Adverse Device Effect (SADE): A serious adverse event that is believed to have been caused by or is associated with the device.

Unanticipated Adverse Device Effect (UADE): Any serious adverse effect on health or safety, or any life-threatening problem or death caused by, or associated with, a device if that effect, problem or death was not previously identified in nature, severity or degree of incidence in the Investigational Plan, or any other unanticipated serious problem associated with a device that relates to the rights, safety or welfare of subjects.

Event Severity: Event severity will be graded in accordance with the guidelines provided in the NCI Common Terminology Criteria for Adverse Events (CTCAE) v 4.0 (NCI, Oct. 2009). For those events that do not have a term identified in the CTCAE, events should be identified using the following criteria:

Mild: Event causes a low level of inconvenience or discomfort, does not interfere with subject's usual activities, and is usually transient; treatment not ordinarily needed for relief of symptoms.

Moderate: Event causes moderate level of inconvenience or discomfort, may interfere with subject's usual activities; new treatment or change in treatment for symptoms may be needed.

Severe/Serious: Event causes severe discomfort and considerable interference with subject's usual activity and requires treatment and/or hospitalization.

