9.1.1 Recording and Reporting of Adverse Events

All study staff are responsible for ensuring that complete safety information has been recorded on the CRF and in source documents. All Adverse Events (AE) must be documented throughout the study. Medical assessments must be performed during each scheduled study visit and serve as the primary basis for identifying AEs. Although spontaneous or elicited medical complaints will likely constitute the majority of AEs, any non-scheduled visit to a healthcare provider or the initiation of a new medication should trigger additional questioning as to the occurrence of an AE.

All adverse events, regardless of severity or relationship to investigational device, will be collected from the time of initiation of fiducial marker placement and through the 18-month visit. Subjects who experience an adverse event related to TraceIT hydrogel will be followed until the adverse event has resolved or until the subject has stabilized and follow-up care has been transferred to the subject's primary care physician.

Any changes in a subject's condition noted prior to the procedure should be adequately assessed and included in the medical history for the subject.

Any event precipitating an intestinal acute CTCAE score of grade 2 or more must be documented as an adverse event.

To the extent possible, the event to be recorded and reported is the event **diagnosis** as opposed to event **symptoms**. Please refer to the following examples:

- Fever, chills, nausea and vomiting in the presence of a clinically diagnosed infection is to be reported as an infection only.
- Pain on urination in the presence of a clinically diagnosed urinary tract infection is to be reported as a urinary tract infection only.

Reporting Serious Adverse Events

All serious adverse events and serious adverse device effects shall be reported to the Sponsor or their representative (by fax or by phone) within 24 hours of the time the investigator learns of the event. A written report detailing the event and signed by the investigator shall be submitted to the Sponsor within 5 working days. The investigator shall notify the reviewing IRB of all serious adverse events occurring in the study according to the IRB's requirements.

Device failures or problems not associated with adverse events will be documented separately on the appropriate case report form. The product should be retained for evaluation.

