3.4.1 Statistical Methods

CEC adjudicated AEs will be summarized by term, by term and procedure/device relationship, and by terms and severity (CTCAE Grade). In addition to the general presentation of safety events, the following will be calculated and reported:

- The number and percentage of subjects who experienced TraceIT administration procedure-related events which result in a delay in initiation of RT
- The number and percentage of subjects with at least one duodenal adverse event presented by grade and timing; i.e., acute (within 3 months) and late (>3 months). A similar presentation will be provided for non-resected subjects only.

Additionally, the numbers and percentages will be calculated for subjects who have developed one or more following events: AEs, SAEs, UADE, SADE, procedure related

AEs, device related AEs, radiation therapy related AEs, duodenal related AEs by site and total.

Adverse event overall listing will include AE CTCAE term, AE CTCAE SOC, onset days since procedure and duration, AE attribution, CTCAE grade and adjudication term, SAE and classification, UADE, action taken, outcome and residual effects.

Single imputation will be implemented for partial start/end dates (missing month and/or day) of adverse events, or concomitant medications.

For the missing start date:

- Only the start day is missing: the 15th day of the month will be used if the resulted imputed date is after the index procedure date; otherwise the procedure date will be used.
- Both the start day and the start month are missing: the 15th day of January will be used if the resulted imputed date is after the index procedure date; otherwise the procedure date will be used.

For the missing end date:

- If the end day is missing, the 15th day of the month will be used if the resulted imputed date is after the corresponding start date; otherwise the last day of the month will be used.
- If end day and end month are both missing, the 15th day of December will be used if the resulted date is after the corresponding start date; otherwise the 31st day of December will be used.

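### Duodenal symptoms are graded before the spacer is placed, but the toxicity tables specify no comparison with that grade, and the grade 2 recording rule does not mention baseline

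*Protocol*

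**What the plan says.** **Collection.** The Protocol Summary (Screening/Baseline) and Protocol 6.4.4 list "Assessment of baseline duodenal symptoms per NCI CTCAE". That visit falls "within 45 days prior to planned TraceIT hydrogel injection". Table 2 in Protocol 6.4.1 also ticks the duodenal-symptom assessment in the index-procedure column. The itemised index-procedure lists in the Summary and in 6.4.5.1 name only adverse events, and nothing places a symptom grade before needle insertion.

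**Recording rules.** Protocol 9.1 defines an adverse event as "Any untoward medical occurrence in a subject that is of new onset or has become worse". Protocol 9.1.1 says that adverse events "will be collected from the time of initiation of fiducial marker placement and through the 18-month visit". It also says "Any changes in a subject's condition noted prior to the procedure should be adequately assessed and included in the medical history for the subject", and separately "Any event precipitating an intestinal acute CTCAE score of grade 2 or more must be documented as an adverse event".

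**Analysis.** SAP 3.4.1, matching Protocol 7.7, reports "The number and percentage of subjects with at least one duodenal adverse event presented by grade and timing", divided at 3 months into acute and late. SAP 3.3.1 reports duodenal toxicity in unresected subjects the same way. Neither mentions the baseline grade. A comparison with baseline is specified for dosimetry and quality of life (SAP 3 and 3.3.1) and for physical examination and vital signs (SAP 5.1.6).

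**Eligibility.** The gastrointestinal symptom exclusion is "Active gastroduodenal ulcer or uncontrolled watery diarrhea", so controlled or milder symptoms can be present at entry.

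**The concern.** The spacer is meant to spare the duodenum, and the study has one arm. The natural reference for a subject's duodenal grade after injection is that subject's own grade before it. The plan collects that grade and then specifies no analysis that sets it beside the later grades.

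Pre-existing symptoms are foreseeable. The protocol's stated reason for adding the word uncontrolled to the diarrhea exclusion is that many patients are on chemotherapy during screening, which can itself cause diarrhea. If a stable symptom of that kind is entered as an adverse event at one site and left in the medical history at another, the reported duodenal incidence depends partly on how the site reads Section 9.1.1. The reader of the table cannot tell.

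**Working it through.** The plan gives no figure to reproduce: there is no sample size calculation, threshold or expected event rate. The check is therefore on the text, followed by a scale calculation.

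**1. The two recording rules, case by case.** The 9.1.1 rule is worded for acute scores, so the table below concerns acute events.

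| Baseline grade | Worst acute grade | Section 9.1 alone | 9.1.1 grade 2 rule, read literally | Where it is tabulated |
|---|---|---|---|---|
| 0 | 2 | event (new) | event | grade 2 |
| 1 | 2 | event (worse) | event | grade 2 |
| 2 | 2, unchanged | not an event | event | grade 2, or absent |
| 0 | 3 | event (new) | event | grade 3 |
| 2 | 3 | event (worse) | event | grade 3 |

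The rules diverge in one row only: the unchanged grade 2 symptom. The last two rows agree on recording, but a rise of three grades and a rise of one grade land in the same cell.

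**2. Does any other output supply the comparison?** The adverse-event listing in SAP 3.4.1 itemises its contents and does not include baseline grade. Medical history (SAP 5.1.3) is tabulated as resolved or ongoing and is not linked to later grades. SAP 3 promises that all data will be tabulated or listed, so the baseline grade should appear somewhere, but no comparison is specified.

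**3. Size of one reclassification.** With n = 6, one subject is 1/6 = 16.7 percentage points. Exact (Clopper-Pearson) 95% intervals:

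- 0/6 = 0% (0% to 45.9%)
- 1/6 = 16.7% (0.4% to 64.1%)
- 2/6 = 33.3% (4.3% to 77.7%)

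For the unresected-only table the step is 1/m, where m is the number unresected. If m were 4, for illustration, it would be 1/4 = 25 points.

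**4. How often could it arise?** The documents give no prevalence of grade 2 or higher duodenal symptoms at baseline. Taking p as an assumption, the chance that at least one of six subjects has one is 1 − (1 − p)^6:

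- p = 10%: 1 − 0.9^6 = 46.9%
- p = 20%: 1 − 0.8^6 = 73.8%
- p = 30%: 1 − 0.7^6 = 88.2%

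At any given p these are ceilings on the problem. The symptom must also persist unchanged, and the site must apply 9.1.1 literally. The documents allow no estimate of either.

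**5. A side effect of date imputation.** Under SAP 3.4.1, a partial start date that does not impute to after the index procedure is set to the procedure date. The SAP 3.4 timing formula then gives (0 + 1)/(365.25/12) = 0.03 months. A pre-existing symptom that has been recorded as an event with a partial onset date would therefore appear as an acute event starting on the procedure day.

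**The case against.** The strongest reply is that baseline already enters when the event is recorded. The tables count adverse events, and 9.1 restricts these to new or worsened occurrences. An unchanged symptom need not be an event precipitating a score, and 9.1.1 sends changes noted before the procedure to the medical history. On that reading 9.1 and 9.1.1 agree. This stands in part. A reader might infer a flat contradiction, but the documents support only an unreconciled ambiguity: the consistent reading is available, the literal one is too, and nothing tells a site which to use.

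A reader might also infer that toxicity could be hidden, or that baseline information is discarded altogether. Neither holds as stated. A worsened symptom is an event under 9.1, so masking would require a site to misjudge it as unchanged. The QLQ-C30 and QLQ-PAN26 symptom scores are compared with each subject's own baseline. Intestinal medication is tabulated with a pre-procedure category (SAP 5.1.5). The Clinical Events Committee classifies each event's relationship, and SAP 3.4.1 reports device-, procedure- and radiation-related events separately. The committee, however, is given no rule for comparing with the baseline grade, and a symptom that a site does not record as an event does not reach its adjudication.

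Finally, no stated decision depends on this table. The named safety endpoint is procedure-related events that delay radiotherapy. That is correct, and it limits the weight of the point.

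**Conclusion.** The point holds in a limited form. The duodenal toxicity outputs specify no comparison with the baseline grade, and the grade 2 rule in 9.1.1 is silent on baseline and not reconciled with 9.1. An unchanged grade 2 symptom can therefore be recorded differently by different sites, and rises of different size share a cell.

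One affected subject moves the incidence by 16.7 points. That is arithmetic on six subjects and needs no assumption. How likely it is cannot be derived from the documents. The 46.9% to 88.2% range rests on an assumed prevalence of 10% to 30% and describes only the precondition, so it should not be read as the chance of a miscount.

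The point bears on the interpretation of an exploratory endpoint and a descriptive safety table, not on technical success or the named safety endpoint. It is a cheap improvement worth making.

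**What to change.** In SAP 3.3.1 and 3.4.1:

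- Define baseline as the last duodenal-symptom grade recorded before the index procedure. This is the screening grade unless an index-day grade was recorded before the procedure; the plan does not clearly schedule one, so it should not be assumed to exist.
- Add a per-subject table of baseline grade, worst acute grade and worst late grade.
- Report the number of subjects with a duodenal grade above baseline beside the unadjusted count. The unadjusted count must stay, because a symptom that resolves after screening and returns at the same grade would not exceed a screening baseline.

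Keep the capture rule in Protocol 9.1.1 as broad as it is; narrowing mandatory recording in an early feasibility study would lose safety information. Reconcile it with 9.1 by stating that grade 2 or higher events unchanged from baseline are recorded and flagged, so that the analysis can separate them.

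The cost is one six-row table, one extra column and a clarifying sentence. The screening grade is already collected. The SAP change can be made under SAP 5.6 before the analyses are run; the sentence in 9.1.1 would go through the amendment route in Protocol 10.3.
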